Viral Conjunctivitis Treatment Study

NCT03861728 IRB STUDY NUMBER: 20170064

VERSION 7, DATE: 11/29/21

1) **Protocol Title**

Treatment of Viral Conjunctivitis with Avenova® (0.01% hypochlorous acid)

2) **Objectives**

The objective of this study is to determine the efficacy Avenova® (0.01% hypochlorous acid) in the treatment of viral conjunctivitis. We hypothesize that patients treated with Avenova® will have a quicker resolution of their ocular signs and symptoms of Viral Conjunctivitis.

3) **Background**

Avenova® is a proprietary pure hypochlorous acid under a family of skin cleansing products by NovaBay that has been approved by the FDA as a 510(k) medical device. Many in vitro studies have evaluated the efficacy of hypochlorous acid against bacterial and viral agents. In ophthalmology, it is commonly used as a lid cleanser in the treatment of blepharitis and meibomian gland dysfunction. It is applied directly to the lid margin and has an excellent skin and ocular safety profile, which includes a lack of ocular irritation on application. (See included supplemental “Material safety data sheet”)

We propose a study to evaluate the role of Avenova® (0.1% hypochlorous acid) in the treatment of common ocular viral infections.

4) **Inclusion and Exclusion Criteria***

Inclusion:

Patients who present to Bascom Palmer Eye Institute with a clinical diagnosis of viral conjunctivitis will be allowed to participate in the study. Patients with viral conjunctivitis will be diagnosed clinically with symptoms of either unilateral or bilateral conjunctivitis of less than 1 week duration. These diagnoses will then be confirmed with a viral PCR. These patients will also need to have one of the following: 1. follicular conjunctivitis of the inferior tarsal conjunctiva, 2. mucoid discharge, 3. preauricular lymphadenopathy, or 4. associated upper respiratory symptoms.

Exclusion:

Patients with a history of allergic conjunctivitis, history of herpetic eye disease, concurrent diagnosis of bacterial conjunctivitis, purulent discharge, intraocular inflammation, or current contact lens use will be excluded from the study. Immunocompromised/Immunosuppressed patients, patients with HIV, pregnant women, prisoners, or adults who are unable to provide consent will be excluded. Age less than 18 years old will be excluded viral conjunctivitis treatment arm of the study.

5) **Number of Subjects***

Total number of subjects to be enrolled is 125

6) **Study-Wide Recruitment Methods***

N/A.

7) **Study Timelines***

Patients will participate for 3 weeks in total. Enrollment will be complete by 2 years and the primary analyses will be completed in 2.5 years duration.

8) **Study Endpoints***

The primary endpoint of the study is the resolution of follicular conjunctivitis and symptomatic improvement in the viral conjunctivitis arm.

9) **Procedures Involved***

Patients will be diagnosed by clinical exam in the Bascom Palmer Emergency Department. Those meeting inclusion criteria will be randomized to Avenova® spray vs artificial tears (placebo), to be used in the affected eye four times a day for two weeks duration in total. Samples of the tears from the ocular surface and conjunctiva will be obtained through cotton swabs from the patient's initial visit and daily to every-other-day through 1 week, and finally at week 2 (e.g. Day 0, 1, 2, 3, 4, 5, 6, 7, and 14 +/- 1 day). These samples will be obtained in both groups (Avenova® spray and artificial tears). Collected samples will be sent to the Bascom Palmer Microbiology laboratory for PCR evaluation and microbiology evaluation and then promptly disposed of. Patients will return once every week for 3 weeks duration in order to assess for resolution of follicular conjunctivitis and symptomatic relief based off the subjective scoring guidelines (see supplemental material) as well as physical exam findings (lymphadenopathy, follicular conjunctivitis, injection, discharge, subepithelial infiltrates, conjunctival pseudomembranes) *See Objective Questionnaire*. Patients will be questioned about adverse effect to treatment each visit and be assessed for surrounding periorbital dermatitis. However, Avenova® has a wide range of indications for use and is approved by the FDA as a medical device for use on the skin.

10) **Data Management***

Viral conjunctivitis

POWER ANALYSIS:

%spontaneous resolution in 7 days: 20%

%Resolution with treatment: 50%

N=39 for each treatment group for power of 80%

Data will include medical record number, diagnosis, type of therapy, commentary on improvement/worsening of signs and symptoms. It will also include adverse events.

Research data can only be accessed by clinicians (whose names have been added to the IRB) in direct care of the patient or those listed on the IRB. All identifiable data will be stored on a locked and encrypted USB drive and will be de-identified of personal identifying information at the conclusion of the study once all data is analyzed, which will again be stored on a locked and encrypted USB drive. The investigatory team will assign subject identifiers and study records will be locked in the office of [name] on the [name] of the Bascom Palmer Eye Institute located at [name].

11) **Provisions to Monitor the Data to Ensure the Safety of Subjects***

Subjects will return for follow up appointments at weekly intervals for three weeks total. It is safe to monitor these patients at these intervals as these viral infections are self-limiting and often resolve with time. As there is currently no treatment for these infections, observation and symptomatic management is standard of practice.

Co-investigators on the study will assess patients at each of the follow-up visits for any side effects (listed in the informed consent) to the assigned medical treatment and document this in the electronic medical health record. Patients will be given the telephone number of a principle investigator if they believe they are having a significant side effect or may also present at the 24 hour emergency department at the Bascom Palmer Eye Institute. If there are noted adverse reactions to the device, participation in the study will be terminated for that individual patient. Data will be analyzed by members of the IRB team at weekly intervals, and if during the study, greater than 20% of patients are observed to have an adverse reaction to the spray, the study will be terminated prematurely.

12) **Withdrawal of Subjects***

Patients will be withdrawn from the study if the physician deems their symptoms to be clinically related to administration of the device. Patients may withdraw voluntarily from the study at any time, but will be continued to be followed for the duration of the study. Non-compliant patients (those who do not take the study device) will be allowed to continue in their respective groups (Avenova® versus artificial tears) for the duration of the study.

13) **Risks to Subjects***

Avenova® (0.1% hypochlorous acid) has been extensively studied and has been approved by the FDA as a 510(k) medical device wound cleanser for any skin and undergone extensive in-vitro toxicity testing. In ophthalmology, it is commonly used as a lid cleanser in the treatment of

blepharitis and meibomian gland dysfunction. It is applied directly to the lid margin and has an excellent safety profile. There has been no noted ocular side effects, which includes a lack of ocular irritation. (see included “Material safety data sheet”)

We see no foreseeable risk to the artificial tear group.

There is no foreseeable risk of obtaining the cotton swabs from the conjunctiva. These tests will be performed without adding additional costs to the patient.

Exclusion criteria include pregnancy and thus this group would not be included in the study. Those who may become pregnant during the study may choose to leave the study—however the topical spray is safe to be used in pregnancy.

14) Potential Benefits to Subjects*

Benefits to patients would include earlier resolution of lesions and discomfort from conjunctivitis compared to control. These treatments could shorten duration of viral conjunctivitis, a common and extremely contagious viral infection that stops patients from carrying out their normal activities. If our study shows a shortened duration of infection from this therapy, it could result in symptomatic relief from the effects of viral conjunctivitis for which there have been no beneficial treatments at present.

15) Vulnerable Populations*

Not applicable

16) Setting

Bascom Palmer Eye Institute is an ophthalmic hospital with a 24 hour emergency department specializing in ophthalmic disease. Research will be collected as the patient is followed in the emergency department as well as by physicians staffing clinic.

17) Resources Available

Bascom Palmer Eye Institute is an ophthalmic hospital with a 24 hour emergency department specializing in ophthalmic disease. The institute receives a wide referral base including all of Florida and the surrounding sites, as well as numerous international referrals due to its prominence in the field of ophthalmology. This institute is staffed with residents, fellows and attending’s, all specialized only in the field of ophthalmology. Each week, the emergency department diagnoses at least 10 cases of viral conjunctivitis. If half of these cases agree to participate in the study, there will be adequate number of patients to power the study.

Before the start of the study, all participating members will be informed of the study, as well as possible risks, benefits and their role within the study.

We plan to devote 24 months to collecting patients as well as the statistical analysis for the study.

18) Recruitment Methods

Patients will be recruited from the Bascom Palmer Eye institute emergency department as a referral. Potential subjects are those identified as being infected with viral conjunctivitis by the ophthalmologist. There will be no advertisements for this study and no payment will be offered to participants of the study. If the patient consents to the study, he/she will be randomly assigned to Avenova® vs artificial tears through a randomization computer program.

19) Confidentiality

Identifiable data will be stored on a locked and encrypted USB drive to be locked in the office of [name] on the [name] of the Bascom Palmer Eye Institute located at [name]. This data will be de-identified of personal identifying information at the conclusion of the study. The investigatory team will assign subject identifiers and study records will only be accessed by the study coordinators.

20) Provisions to Protect the Privacy Interests of Subjects

To limit intrusiveness to patients, data will only be collected during clinic follow-up (once every week for three weeks). Patients will receive a subjective questionnaire (see supplemental material) each visit to ensure consistency between patients and between visits. The research team will then review the data collected through these questionnaires for analysis.

21) Compensation for Research-Related Injury

Patients will not be compensated for research related injuries. This will be written in the consent and described to the patient before participation in the study.

22) Economic Burden to Subjects

The device will be provided free of cost to patients as provided by Novabay. Also, there is no cost to participants for the collection of tears via the use of cotton swab.

23) Consent Process

Consent will be obtained during an Emergency Room visit by the physician and will follow the SOP: Informed Consent Process for Research (HRP-090). The informed consent will occur that same visit to the ER; if the patient decides that he/she does not want to participate, he/she will be unable to participate at a later visit. Each visit, the patient will be asked and have the option to leave the study.

Non-English Speaking Subjects

- Spanish will be used to obtain consent in those who prefer the Spanish language—translation will be offered if needed with consent offered in the Spanish language.

24) **Process to Document Consent in Writing**

Eligible subjects will be informed of the nature, risks, and benefits of the study and informed that they are not required to participate. If interested in participating, they will be given the consent form to read, asked if they have any questions or need further explanations, and will have the option of taking the consent form home to have more time to decide about participating.

The consent process will be obtained by one of the research team members whose name and signature will be mentioned in the consent form. The details of the study will be explained to the prospective subjects.

25) **Drugs or Devices**

The device will be stored, handled and dispensed by the Bascom Palmer Pharmacy and the designated IRB study team members. The device will be administered by the patient. Avenova® has received FDA approval as a 510(k) medical device with a wide range of indications including for use on the skin surface. Note: although Novabay has been described as a funding source, only Avenova® will be provided, no direct funding will be provided.

References

2. Debabov D, Noorbakhsh C, Wang L, et al. Avenova™ with Neutrox™ (pure 0.01% HOCl) compared with OTC product (0.02% HOCl). NovaBay Pharmaceuticals, Inc., Emeryville, California, USA.

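### The plan makes no provision for using days since symptom onset, a plausibly prognostic baseline value; adjusting for it would be a cheap gain in precision, not the repair of an error

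*Combined protocol and SAP*

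**What the plan says.** - **Entry (section 4).** Patients qualify with "symptoms of either unilateral or bilateral conjunctivitis of less than 1 week duration", plus at least one of four further findings. Duration is used only as a threshold.
- **Natural history (section 11).** The protocol says that "these viral infections are self-limiting and often resolve with time".
- **Endpoint (section 8).** Clearing of follicular signs and better symptoms. No time point and no method of analysis are given.
- **Power statement (section 10).** Control: "spontaneous resolution in 7 days: 20" percent. Active: "Resolution with treatment: 50" percent. Size: "N=39 for each treatment group for power of 80" percent. No test, significance level or covariate is named.
- **Enrolment (section 5).** "Total number of subjects to be enrolled is 125".
- **Allocation (section 18).** Patients are "randomly assigned to Avenova® vs artificial tears through a randomization computer program". No stratification factor is mentioned.
- **Data items (section 10).** The list includes neither onset date nor duration. The scoring sheets are in supplementary material that was not available for this review.

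**The concern.** Entry can fall anywhere from day 0 to day 6 of the illness, so an assessment 7 days later falls on illness day 7 for one patient and day 13 for another. In an infection that clears by itself, that spread probably explains part of the variation in who has recovered.

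Two things are at stake. A raw comparison leaves this variation in the error term, which costs precision. And if one arm happens to enrol later in the illness, the raw difference moves with that imbalance and nothing in the plan corrects it. If the number of days is not recorded at entry, it may not be recoverable later, and an adjustment chosen after the results are known carries less weight.

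**Working it through.** **1. Reproduce the plan's figure.** Inputs from section 10: 20%, 50%, 80% power. Two-sided 5% is assumed because it reproduces the stated size.

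n = [1.960 × √(2 × 0.35 × 0.65) + 0.842 × √(0.20 × 0.80 + 0.50 × 0.50)]² / 0.30²
= (1.322 + 0.539)² / 0.09 = 38.5, so **39 per arm**, as stated.

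Power at 39 per arm is 80.5%. At 125 / 2, about 62 per arm, it is about 95%.

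**2. Chance imbalance in duration.** The documents give no distribution of entry day, so days 0 to 6 are assumed equally likely (SD 2.0). The SD of the difference in arm means is 2.0 × √(2/n).

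| | 39 per arm | 62 per arm |
|---|---|---|
| SD of difference (days) | 0.45 | 0.36 |
| Trials differing by ≥ 0.5 day | about 27% | about 16% |
| Trials differing by ≥ 0.75 day | about 10% | about 4% |

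**3. Power with and without adjustment.** Trials were simulated with overall rates held at 20% and 50%. The slope, in log-odds of resolution per extra day since onset, is assumed. The raw two-proportion test is compared with the likelihood-ratio test for treatment in a logistic regression on treatment and days.

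| Assumed slope | 39: raw | 39: adjusted | 62: raw | 62: adjusted |
|---|---|---|---|---|
| 0 | 82% | 82% | 95% | 95% |
| 0.2 | 81% | 82% | 95% | 95–96% |
| 0.4 | 81% | 85–86% | 95% | 97% |
| 0.6 | 81% | 90% | 94–95% | 98% |

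The gain is about 0 to 9 points at 39 per arm and 0 to 4 at 62. Ranges show the spread between runs that took entry as days 0–6 or 0–7.

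**4. Precision and bias given imbalance, using the standardised risk difference.** This is a separate simulation of 10,000 trials per scenario, with slopes written as odds ratios per day (1.25, 1.5 and 2.0 are log-odds 0.22, 0.41 and 0.69). The last two columns are for 39 per arm.

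| Odds ratio per day | Variance, adjusted / raw | Shift in raw difference per day of imbalance | Shift for half a day |
|---|---|---|---|
| 1.0 | 1.01 | 0 points | 0 |
| 1.25 | 0.97 | 4.8 points | 2.4 |
| 1.5 | 0.90 | 7.9 points | 4.0 |
| 2.0 | 0.76 | 11.3 points | 5.7 |

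The half-day column is 0.5 times the column before it. After adjustment the shift per day of imbalance is at most 0.3 points.

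**5. Type I error at 39 per arm, both arms at 20%.** Raw test: 4.6% to 5.3%. Adjusted standardised risk difference with a normal critical value: 5.3% to 5.8%. The likelihood-ratio test also lies at about 5 to 6%.

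**The case against.** The strongest reply is that nothing here is wrong. Randomisation makes the raw comparison valid, its type I error is close to 5%, and 39 per arm is correct for the stated rates. At the planned enrolment power is already about 95%, so at most about 4 points remain to be gained. All of that stands.

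The prognostic strength is also assumed. The documents offer only a qualitative statement. A patient still symptomatic on day 6 may be a slow resolver, so even the direction is not assured. That stands too, and it is why slope zero is included. The model would estimate the relation in either direction, and the price if there is none is about 1% more variance.

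A reader might infer more than the documents support:

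- *That the sponsor decided against adjustment or stratification.* The protocol names no primary analysis at all; this is silence, not a choice.
- *That Day 7 is the primary time point.* Seven days appears only beside the control rate in the power statement. Weekly review for three weeks, and a hypothesis about speed of recovery, would fit other analyses.
- *That duration is already in the dataset.* It must be asked to apply the entry rule, but a yes or no suffices for that and the data list omits it.
- *That the trial is seriously exposed.* At slope 0.4 and 39 per arm, raw power falls to 54%, against 80% adjusted, when imbalance of at least 0.75 day runs against Avenova. That is half of the 10% in step 2, about 5% of trials, and about 2% at 62 per arm.

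In the other direction, section 4 has diagnoses confirmed by PCR after clinical diagnosis, and no allowance for PCR-negative patients or dropout is stated. The number analysed may fall below 125, so 39 and 62 per arm are shown as the two sizes the documents give.

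**Conclusion.** The point holds as an efficiency improvement. The plan provides no way to use a baseline value that must be ascertained at entry and is plausibly related to outcome. It does not hold as a claim that the planned comparison is invalid, that the sample size is wrong, or that onset is known to be a strong predictor.

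The power gain is modest at 39 per arm and small at 62. The firmer benefit is protection of the single trial that is run: a half-day imbalance, which is not rare at either size, would shift the raw difference by about 2 to 6 points against a planned 30 if onset is prognostic over the odds-ratio range shown.

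These sizes rest on assumptions absent from the documents: entry days equally likely, a linear log-odds slope, a two-sided 5% test, 1:1 allocation, no dropout, and outcome assessed at 7 days.

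**What to change.** 1. Record days since symptom onset as a number at Day 0, on the case report form.
2. State the primary time point, for example the 7 days used in the power statement.
3. Prespecify a logistic regression of resolution on treatment and days since onset, with the treatment effect tested by likelihood ratio. Report it as a standardised risk difference with 95% CI, using a small-sample variance correction, beside the raw proportions. The risk difference keeps the result on the scale of the 20% against 50% planning assumption.
4. For the symptom-score component, adjust for the Day 0 score, and confirm that the questionnaire is completed at that visit.
5. Check the type I error of the chosen procedure by simulation at the number expected to be analysed.

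**Cost.** One added data field and slightly more analysis work; no extra patients or visits. If onset is not prognostic, variance rises by about 1%. Without a small-sample correction, type I error at 39 per arm is about 5 to 6%.

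### Does the lack of a rule for PCR-negative patients who are randomised undermine the analysis or the sample size?

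*Combined protocol and SAP*

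**What the plan says.** Section 4 admits patients on the clinical picture and then adds, still under Inclusion: "These diagnoses will then be confirmed with a viral PCR". It gives no timing for the test and no consequence of a negative result.

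Section 9 has the diagnosis made by examination in the emergency department and continues: "Those meeting inclusion criteria will be randomized to Avenova® spray vs artificial tears (placebo"). Swabs start at the initial visit and are taken in both groups. On their handling it says: "Collected samples will be sent to the Bascom Palmer Microbiology laboratory for PCR evaluation and microbiology evaluation". No turnaround time is given. Section 18 ties allocation to consent: "If the patient consents to the study, he/she will be randomly assigned to Avenova® vs artificial tears through a randomization computer program". Section 23 places consent at the same emergency visit, although Section 24 lets the patient take the form home.

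Section 12 covers device-related symptoms ("Patients will be withdrawn from the study if the physician deems their symptoms to be clinically related to administration of the device"), voluntary withdrawal and non-compliance. It does not mention a negative PCR. The data list in Section 10 reads "Data will include medical record number, diagnosis, type of therapy, commentary on improvement/worsening of signs and symptoms", plus adverse events. No analysis set is defined.

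On size, Section 10 assumes 20% resolution without treatment at 7 days and 50% with it, and states "N=39 for each treatment group for power of 80" per cent. Section 5 states "Total number of subjects to be enrolled is 125". The two figures are not linked.

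**The concern.** PCR confirmation is listed as an entry condition, yet the order of events described (examination, consent, allocation, swab to the laboratory) lets a patient be randomised before the result is known. Some randomised patients may then prove PCR-negative, and the plan does not say whether they count.

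The choice could matter in three ways. If PCR-negatives stay in and the product does nothing for them, the observed difference shrinks and power falls. If they are left out, the sample shrinks. If the decision is taken after outcomes are seen, it could be made to suit the result. The unexplained step from 78 to 125 adds to the doubt, because a reader cannot tell whether the surplus was meant to cover such patients.

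**Working it through.** **Inputs.** From Section 10: 20% v 50%, 80% power, 39 per group. From Section 5: 125 enrolled. Assumed because not stated: two-sided 5%, 1:1 allocation, and a single yes/no resolution outcome at 7 days. The PCR-negative share f and the resolution rates in PCR-negatives (c in control, t in treated) are also assumptions, so they are varied.

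**The plan's own figure.** Pooled-variance formula, mean rate 0.35:

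n = [1.960 × √(2 × 0.35 × 0.65) + 0.842 × √(0.2 × 0.8 + 0.5 × 0.5)]² / 0.30² = (1.322 + 0.539)² / 0.09 = 38.5, so 39 per group.

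This matches. Exact power of the pooled z-test is 81.3% at 39 per arm. With all 125 (62 control, 63 treated) it is 95.2%.

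**Room between 78 and 125.** 2 × 39 = 78, and 1 − 78/125 = 37.6%. So 125 still leaves 78 patients if up to 37.6% are PCR-negative or lost.

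**Policy A: keep everyone randomised.** The arm rates become (1 − f) × 0.20 + f × c and (1 − f) × 0.50 + f × t. For example, f = 20% with c = t = 0.20 gives 20% v 44%.

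**Policy B: Day-0 PCR-positives only, as randomised.** The rates stay at 20% v 50%. The numbers per arm are 125 × 0.8 / 2 = 50, 125 × 0.7 / 2 = 43.75 (43–44), and 125 × 0.624 / 2 = 39.

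| Share PCR-negative | A: no effect, both arms 20% | A: no effect, both arms 50% | A: half benefit, 20% v 35% | B: PCR-positives only |
|---|---|---|---|---|
| 20% | 83.4% | 80.1% | 90.6% | 89.5% |
| 30% | 73.3% | 67.7% | 87.4% | 85.5–86.4% |
| 37.6% | 63.9% | 56.9% | 84.4% | 81.3% |

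Under policy A, power reaches 80% at f = 23.7% (negatives resolving at 20% in both arms), 20.1% (at 50% in both arms) and 47% (half benefit).

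**With 10% also lost** (56 per arm) and f = 20%, policy A with no effect in negatives gives 79.3% or 75.1%. Policy B gives 86.8% (45 per arm).

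**If 20% v 50% already describes all clinically diagnosed patients,** policy A has no dilution and power is 95.2%. If the effect is also the same in PCR-positives and PCR-negatives, policy B costs power: 95.2% falls to 89.5%, 85.5–86.4% or 81.3% at the three shares.

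**Reading the passages together.** Section 4 can mean that entry is clinical and PCR only documents the diagnosis. A PCR-negative patient is then an ordinary participant, which fits Section 12's silence and its retention of non-compliant patients. Alternatively, Section 9's reference to the inclusion criteria can take in PCR, and a PCR-negative patient is never randomised. Each reading gives a workable analysis.

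**The case for a change.** The strongest argument for a change is selectivity. PCR is run on serial swabs from Day 0 to Day 14, and the plan does not say which one confirms the diagnosis. The product is being tested partly because of reported in vitro activity against viruses, so later results could be affected by treatment. Choosing patients on those results would bias the comparison, and with no written rule the choice could follow the data. In the no-effect case at 37.6% negative, keeping or dropping these patients moves power from 57–64% to 81%.

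Part of this stands. The sentence in Section 4 is ambiguous, no analysis set is named, and only a swab that allocation cannot influence gives a fair subgroup. But an analyst who defaults to all patients as randomised, or who uses the baseline swab, avoids the bias. The large power gap needs both no benefit in PCR-negatives and a high share of them, and nothing in the documents suggests either.

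The obvious remedy, a PCR-positive primary set with all randomised patients as a sensitivity analysis, is not clearly better. It narrows the conclusion to confirmed cases and costs power when the effect is the same in both groups. If the swab were required only before first use of the product, it could be taken, missed or inadequate after allocation is known, and no masking is described. Exclusions could then depend on the arm.

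The remaining points carry little weight. The Section 10 data list is not worded as exhaustive, and its diagnosis entry can hold the PCR result. The step from 78 to 125 is unexplained with or without PCR, and any rationale supplied for it here would be invented.

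**Conclusion.** The concern describes an unwritten policy, not an error. The 39 per group is right for its inputs, and 125 exceeds 78 by 47. Either sensible way of handling PCR-negatives gives a fair comparison: all randomised, or Day-0 positives as randomised with the swab independent of allocation. Power is below 80% only under policy A, with no benefit in PCR-negatives and a share above about 20–24% (somewhat lower with 10% lost), or under policy B once PCR-negatives and losses together exceed 37.6%. The documents give none of these shares.

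Stating whether PCR gates randomisation, and which population 20% v 50% describes, would record intent and help a reader, but it would correct nothing. Making PCR-positives the primary set is a trade-off with a cost of its own. All the power figures rest on two-sided 5%, 1:1 allocation and a yes/no outcome at 7 days. The primary endpoint in Section 8 combines follicular resolution with symptomatic improvement and gives no time point, so the percentages are indicative. On this basis no change to the plan follows.

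### Current hypochlorous acid users are not excluded, and the protocol body neither restricts nor lists for recording other eye products used during follow-up

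*Combined protocol and SAP*

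**What the plan says.** **Product already in use.** Section 3 says of Avenova: "In ophthalmology, it is commonly used as a lid cleanser in the treatment of blepharitis and meibomian gland dysfunction". Section 13 repeats this.

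**Entry.** Section 4 admits patients with "symptoms of either unilateral or bilateral conjunctivitis of less than 1 week duration". Its exclusions start with "Patients with a history of allergic conjunctivitis, history of herpetic eye disease, concurrent diagnosis of bacterial conjunctivitis, purulent discharge, intraocular inflammation, or current contact lens" wear. They continue: "Immunocompromised/Immunosuppressed patients, patients with HIV, pregnant women, prisoners, or adults who are unable to provide consent will be excluded". Age under 18 completes the list. No prior or current eye treatment appears, and neither study product is named.

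**Follow-up.** Section 9 sets out the two arms, Avenova spray and artificial tears, and is silent on any other eye product. The weekly examinations look for "lymphadenopathy, follicular conjunctivitis, injection, discharge, subepithelial infiltrates, conjunctival pseudomembranes". Section 11 says: "As there is currently no treatment for these infections, observation and symptomatic management is standard of practice". That symptomatic management is neither defined nor limited. Section 12 keeps non-compliant patients in their groups without saying what else they may use.

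**Records.** Section 10 says: "Data will include medical record number, diagnosis, type of therapy, commentary on improvement/worsening of signs and symptoms", and adds adverse events. Next to the diagnosis, the therapy item most naturally means the assigned arm. The questionnaires named in Sections 9 and 20 are supplements that are not in the text.

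**The concern.** The trial tests a product that some eligible patients may already own. A patient with blepharitis who uses it can be enrolled, randomised to artificial tears, and carry on. Another control can buy it after entry. Either way, part of the control arm receives the test product and the measured difference shrinks.

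A second route works differently. The protocol describes no blinding, and a spray is compared with tears. Patients or clinicians who know the arm may add other eye treatment more readily in one arm than in the other. If that treatment affects follicles or symptoms, the two parts of the primary endpoint in Section 8, the difference between arms is biased, and the direction cannot be known in advance.

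Unless other products are recorded with dates, the analyst cannot tell how much of either happened.

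**Working it through.** **Inputs.** Section 10: resolution 20% without treatment (at 7 days) and 50% with it, 39 per group, 80% power. Section 5: 125 to be enrolled. Assumed, because the documents do not state them: two-sided 5% test, 1:1 allocation, every crossover rate below, and full Avenova effect in controls who use it.

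**Step 1: reproduce the plan's figure.** With pooled variance and no continuity correction,

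n = [1.960 × √(2 × 0.35 × 0.65) + 0.842 × √(0.20 × 0.80 + 0.50 × 0.50)]² / 0.30²

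= (1.322 + 0.539)² / 0.09 = 38.5, so 39 per group, as stated. The sample size itself is sound on these assumptions.

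**Step 2: control crossover.** If a share c of controls gains the full effect, the control rate is 0.20 + 0.30c and the difference is 0.30(1 − c). Power is by exact enumeration of the pooled two-proportion z test, with 62 controls and 63 Avenova patients in the last column.

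| c (assumed) | Control rate | Difference (points) | Power, 39 per group | Power, all 125 |
|---|---|---|---|---|
| 0% | 20% | 30 | 81% | 95% |
| 5% | 21.5% | 28.5 | 76% | 93% |
| 10% | 23% | 27 | 71% | 89% |
| 20% | 26% | 24 | 60% | 80% |

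Reversing the 62/63 split lowers the last column by about one point or less.

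**Step 3: bias that differs by arm.** Suppose Avenova has no effect, but treatment added in the Avenova arm alone lifts its resolution from 20% to 26%. The 6 points are chosen only to show the mechanism. The chance of a significant result favouring Avenova, nominally 2.5%, becomes about 9% at 39 per group and about 12% at 62 per group (normal approximation). Enlarging the trial raises this error, whereas in Step 2 it restored power. The same gap in the control arm would hide a real benefit.

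**The case against.** Several objections stand in whole or in part.

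- **Artificial tears in the Avenova arm.** A reader might infer that crossover of either product pulls the arms together. It does not. An Avenova patient who adds tears is on Avenova plus tears against tears. If tears ease symptoms, this removes a comfort advantage of the control arm. If they are inert, nothing changes. Only hypochlorous acid use by controls clearly dilutes.
- **Sample size.** A reader might conclude from the 39-per-group figures that the trial becomes underpowered. Section 5 plans 125, and with all of them analysed even 20% crossover at full effect leaves about 80%. Losses could lower that number, but the documents give no rate.
- **Use before entry.** Randomisation balances it on average, so it is not a bias in itself. It matters because nothing stops it continuing in the control arm.
- **Size of effect of other treatment.** Section 11 says no treatment exists for these infections, and Section 14 says none has been beneficial. No passage supports a particular resolution rate on added treatment. Nor is lid-margin use shown to equal study use in the affected eye, so full effect in Step 2 is an upper assumption.
- **Timing.** Treatment prompted by a finding at the first weekly visit would normally start after 7-day status had been observed. Section 8 fixes no endpoint day, so later assessments remain exposed.
- **Recording.** A reader might infer that nothing is recorded. The therapy item could be read broadly, treatment prescribed at the institute may be traceable through the medical record, and a questionnaire might already ask. What remains is that the protocol body specifies no such record, and products bought by the patient are the likeliest to be missed.

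**Conclusion.** The gap is real, and a cheap improvement is worth making. As written, the plan can enrol current users of the test product, randomise them to the control arm, and specify no record from which crossover could be identified.

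Its size is uncertain. Dilution at the assumed rates of 5% to 20% costs about 5 to 21 points of power at 39 per group, but leaves about 80% or more if all 125 are analysed. Bias from added treatment that differs by arm is not reduced by enrolling more patients. The documents give no rate from which to estimate it.

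Two stronger conclusions are not supported. The documents do not show that the result will be biased or which way. Nor do they justify scoring every patient who receives added treatment as unresolved: if such treatment is given more readily in one arm, that rule can itself create a difference, by marking as failures patients who would have resolved.

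**What to change.** 1. **Section 4:** add current use of any hypochlorous acid eyelid or eye product to the exclusions.
2. **Sections 9 and 10:** at Day 0 and each weekly visit, in both arms, ask about every other eye product used, including those the patient bought, with start date and reason. Add this to the data list. If a questionnaire already asks, say so and list the item.
3. **Analysis:** keep the primary comparison by randomised group with observed status. Add a sensitivity analysis that takes account of patients who used the other arm's product or another eye treatment before the endpoint visit.

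Which added treatments are permitted is for the investigators to decide; these changes cover entry, recording and analysis only.

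The cost is a short amendment, the loss of a few current users from enrolment, and one more question at visits that already include a questionnaire.
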